## 9. Type and Number of Experimental Subjects

Subjects include patients over age 18, excluding pregnant women (self-reported), with an RA diagnosis, or other autoimmune disease to be used as a control. 200 donors will be treated with methotrexate, plaquenil and/or prednisone (DMARDs) that either achieve remission (DAS28<2.6) or do not achieve remission (DAS28>2.6). 50 donor will be utilized as they respond to DMARDs and achieve remission (DAS28<2.6) and 150 donors that do not respond to DMARDs will be treated with DMARDs such as methotrexate, plaquenil and/or prednisone and Cimzia provided to us by UCB. Subjects that fulfill the eligibility criteria will be identified by their physician/rheumatologist to be consented in participating in the study.

## 10. Description of Statistical Analysis to which the Data will be Subjected

For RA blood, using paired t tests, a sample size of 200 subjects will have a 80% power to detect the difference with effect size of 1.25 or above.

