#### 2. Protocol Methodology

**Detection of IL-7 and IL-7R expression levels in RA patients with active and inactive disease:** RA patients will be referred and informed written consent will be obtained by [name]. Blood samples will be collected from patients that have been diagnosed with RA based on ACR classification criteria. The study will include 200 donors. The total number of subjects are divided into two groups to yield a power of 95% at a type I error 5% level [determined based on the preliminary data]. In the first group, 200 donors will be treated with methotrexate, plaquenil and/or prednisone (DMARDs) that either achieve remission (DAS28<2.6) or do not achieve remission (DAS28<2.6). 50 donor will be utilized as they respond to DMARDs and achieve remission (DAS28<2.6) and 150 donors that do not respond to DMARDs will be transferred to second group. In the second group, 150 donors will be treated with methotrexate, plaquenil and/or prednisone and Cimzia® (provided to us by UCB).

In the first group of patients, blood samples will be obtained from RA patients treated with Disease modifying anti rheumatic drugs (DMARDs) such as methotrexate, plaquenil and/or prednisone that achieve remission (DAS28<2.6). The patients that achieve remission (DAS28<2.6), blood will only be taken once at the patients routine visit.

The second group will consist of RA patients that did not respond to "DMARDs". These patients will further receive (DMARDs) such as methotrexate, plaquenil and/or prednisone as well as Cimzia® (provided to us by UCB) free of charge. Cimzia® is a FDA approved drug and is a standard of care. Blood samples will be obtained from the patients treated with DMARDs including methotrexate, plaquenil, and/or prednisone and Cimzia® (provided to us by UCB) that have inactive remission (DAS28<2.6). In this group, blood samples will be collected onset of the study as well as 3 and 6 months after treatment with Cimzia at patient's visit through our collaboration with the aforementioned rheumatologists. Patients receiving intra-articular steroid injections will be excluded from the study.

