PB mononuclear cells will be isolated from RA whole blood and drawn into EDTA or CPT tubes and isolated by Histopaque gradient centrifugation. Monocytes will be isolated from RA PB mononuclear cells by negative selection (as shown in the preliminary data) and half of the monocytes will be differentiated to macrophages for 7 days. The expression levels for IL-7 and IL-7R will be determined by real-time RT-PCR and FACS analysis.

In our statistical analysis, we will first perform a stratified analysis to evaluate the differential expression levels in RA patients with active and inactive disease, controlling for the type of treatment. Data analysis will be performed in collaboration with an UIC Center for Clinical and Translational Science statistician. Specifically, we will perform the comparison of IL-7 and IL-7R expression among RA patients with active (DAS28>2.6) vs. inactive disease (DAS28<2.6) for DMARDs group (group 1). We will then perform a similar comparison for the DMARDs and Cimzia® therapy group (group 2). The stratified analysis can adjust for the potential confounding effect of treatment received and allows for the detection of the potential differential relationships between expression levels of IL-7 or IL-7R and disease status. We will also perform a pooled regression analysis in which the expression logarithm of IL-7 or IL-7R from patients is regressed on the treatment group indicator [DMARDs (group 1) versus on DMARDs plus Cimzia® therapy (group 2)] and disease status (active or inactive disease) which would demonstrate the interaction between treatment groups and disease activity. Such an analysis pools subjects from two treatment groups together and can therefore increase the sample size, and hence potentially the power of detecting the relationships between biomarkers and disease status. The RA samples will be collected over a 2 year period and the data will be analyzed in the last year of the proposal.

**Measure outcomes:** For any of the genes that demonstrate at least 2.5 fold increase (89% sensitivity calculated based on our preliminary data) in active disease compared to remission, correlation coefficient will be calculated for that gene expression level, rheumatoid factor, Cyclic Citrullinated Peptide Antibody (anti-CCP), C-Reactive Protein (CRP), DAS28 and disease duration.

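### Section 10's power statement (200 subjects, paired t tests, effect size 1.25, 80%) does not reproduce as a standardised effect, leaves the pair undefined, and is not reconciled with the 95% in section 2

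*Combined protocol and SAP*

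**What the plan says.** Section 10 is a single sentence about blood samples from RA patients. It states: "using paired t tests, a sample size of 200 subjects will have a 80% power to detect the difference with effect size of 1.25", and extends the claim to larger effects. It gives no alpha, sidedness, SD, scale, endpoint or definition of the pair.

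Section 2 says that the split into two groups is meant "to yield a power of 95% at a type I error 5% level [determined based on the preliminary data", again for 200 donors in total. No effect size, SD or test accompanies that figure.

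The sampling schedule is also in section 2. Fifty donors are in remission on DMARDs, and "150 donors that do not respond to DMARDs will be transferred to second group". For the remitters: "The patients that achieve remission (DAS28<2.6), blood will only be taken once at the patients routine visit". For the Cimzia group: "blood samples will be collected onset of the study as well as 3 and 6 months after treatment with Cimzia". In the laboratory, "half of the monocytes will be differentiated to macrophages for 7 days".

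The planned analyses in section 2 are a "comparison of IL-7 and IL-7R expression among RA patients with active (DAS28>2.6) vs. inactive disease (DAS28<2.6) for DMARDs group (group 1"), then "We will then perform a similar comparison for the DMARDs and Cimzia® therapy group (group 2"), and a pooled regression of log expression on treatment group and disease status that is meant to show their interaction. No paired test is named for any of them.

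**The concern.** In a t-test power statement with no unit attached, an effect size is ordinarily a standardised difference. An effect of 1.25 SD is very large, and 200 pairs would detect it almost with certainty, so 80% looks wrong at once. The number 200 also cannot be a count of before/after pairs, because 50 of the 200 donors give blood once. A second power figure, 95%, is attached to the same 200 donors elsewhere.

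This matters because section 10 is the only place that ties the sample size to a test and an effect size. If that sentence cannot be reproduced, a reader cannot tell what difference each planned comparison can detect, or which comparison the 80% and the 95% are meant to cover.

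**Working it through.** **Inputs.** N = 200, effect size 1.25, 80% power and a paired t test (section 10); alpha 5% and 95% power (section 2); 50 remitters sampled once and 150 Cimzia patients sampled at three times (section 2). Sidedness is not stated; two-sided is assumed.

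**Formula.** For n pairs and standardised effect d (mean difference divided by the SD of the differences), power = P(T > t_crit), where T is noncentral t with n − 1 degrees of freedom and noncentrality d × √n, and t_crit is the 97.5% point of the central t.

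**Step 1: the plan's own figure.** With d = 1.25 and n = 200, the noncentrality is 1.25 × √200 = 17.7 against t_crit = 1.97. Power is about 100%, not 80%.

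| Pairs | Power at d = 1.25 |
|---|---|
| 7 | 78.6% |
| 8 | 85.6% |
| 11 | 96.1% |
| 200 | about 100% |

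Other choices do not rescue it. One-sided, 6 pairs suffice for 80%. With 50, 100 or 150 pairs, or two samples of 50 v 150 or 100 v 100, power at 1.25 exceeds 99.9%. A Bonferroni correction for 20,000 tests still needs only 30 pairs for 80%.

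**Step 2: what 200 pairs detect.** Solving for d gives 0.199 at 80% power and 0.256 at 95%. With one test, one alpha and one N, the two stated powers therefore need different effects.

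**Step 3: other scales.** The SD of paired log2 differences that makes 80% correct is the effect divided by the detectable d (0.1991 for 200 pairs, 0.2302 for 150).

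- 1.25-fold: log2(1.25) = 0.322. 0.322 / 0.1991 = 1.62 with 200 pairs; 0.322 / 0.2302 = 1.40 with 150.
- 1.25 log2 units (2^1.25 = 2.38-fold): 1.25 / 0.1991 = 6.28 with 200 pairs; 1.25 / 0.2302 = 5.43 with 150.

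The documents give no SD, so neither reading can be confirmed or excluded.

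**Step 4: how many pairs exist.** Before/after treatment: 200 − 50 = 150 at most. Monocyte/macrophage pairs could exist in all 200, but no comparison of cell types is planned.

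**Step 5: detectable effects for the planned comparisons.** For two independent samples the noncentrality is d / √(1/n1 + 1/n2), with n1 + n2 − 2 degrees of freedom. All figures are two-sided 5%, before dropout, assay failure and multiplicity. The group 2 splits are assumptions; the documents give no remission rate on Cimzia.

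| Comparison | d at 80% | d at 95% |
|---|---|---|
| Active v inactive, 50 v 150, two-sample | 0.46 | 0.59 |
| Before/after Cimzia, 150 pairs | 0.23 | 0.30 |
| Group 2 between patients, 15 v 135 | 0.77 | 0.99 |
| Group 2 between patients, 75 v 75 | 0.46 | 0.59 |
| Group 2 within patients, 15 pairs | 0.78 | 1.00 |
| Group 2 within patients, 75 pairs | 0.33 | 0.42 |

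Paired rows are in SDs of the difference and two-sample rows in between-patient SDs, so the two kinds cannot be compared directly.

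**The case against.** **The scale is not stated.** The protocol reports its own effects as folds (45-fold and 10-fold in section 1, a 2.5-fold threshold in section 2), so 1.25 might be a fold change. This stands in part. What is certain is that the sentence is underspecified; the arithmetic failure holds on the standardised reading only.

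**A paired test may fit the plan.** A reader might infer that the paired t test matches none of the planned comparisons. The documents do not support that. Group 2 patients enter as DMARD non-responders, whose disease section 9 describes as DAS28 above 2.6, and are sampled at onset, 3 and 6 months. Those who later reach remission supply both an active and an inactive sample, so the group 2 comparison could be within patients. Section 2 simply does not say whether it is.

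**The 95% may be properly derived.** A reader might take 80% and 95% as a contradiction, or take the 95% as unsupported. Neither follows. The figures may cover different tests or effects, and the preliminary data on which the 95% rests are not in the supplied text. What stands is that the inputs are not shown and the two figures are not linked.

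**The consequence is limited.** This also stands. On the standardised reading the sentence understates power.

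**Conclusion.** The point holds, as a defect to be corrected in the justification of the sample size. On the ordinary standardised reading, section 10 is wrong as written: 8 pairs suffice for 80% power at 1.25, and 80% with 200 pairs corresponds to about 0.20, roughly one sixth of the stated effect (0.199 / 1.25 = 0.16). This rests on alpha 5% carried over from section 2 and on a two-sided test, though a one-sided test does not change the conclusion. The fold-change and log-unit readings remain open for want of an SD.

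It also holds that the pair is undefined, that before/after treatment pairs number at most 150, and that neither power figure is assigned to a comparison. A reader might conclude that the study is too small. Nothing here shows that: whether any comparison lacks power depends on target effects, SDs and a group 2 remission split that the documents do not give.

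**What to change.** Replace the sentence in section 10 with detectable effects for the comparisons in section 2, each with its test, alpha and sidedness, effect scale and SD, pair definition where relevant, and available N. The figures in the last table above can be used, subject to these points:

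1. **Active versus inactive, 50 versus 150**, two-sample on log expression. The figures apply if the onset samples of the 150 non-responders form the active group; the plan must say so or name another active group.
2. **Before/after Cimzia.** If intended, add this comparison to the analysis text in section 2, with up to 150 pairs.
3. **Group 2 active versus inactive.** State whether it is between patients at one post-treatment visit or within patients who reach remission, and give the expected remission split. The figures for 15 and 75 remitters only illustrate the range.
4. **Pooled regression.** State the detectable interaction once the split is given, and account for repeated samples if more than one per patient is used.

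In section 2, show the effect size, SD and test behind the 95% and name the comparison it covers. Withdraw the figure only if these cannot be shown.

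The cost is one rewritten sentence in section 10, disclosure of the inputs to one figure in section 2, and a few clarifying lines in the analysis text. Enrolment does not change.

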## 11. Potential Risks and Benefits to Subjects

The risks associated with blood draw include fainting, pain, a bruise at the site of vein puncture, inflammation of the vein. Every care will be taken to avoid these complications. The side effect of the drug Cimzia are similar to other 3 TNF-blockers these include serious infections, Invasive fungal infections, cases of lymphoma and other malignancies, Heart failure, Hepatitis B virus reactivation and Lupus-like syndromes.

Use of Cimzia may cause damage to the fetus. Therefore, it is recommended that patient practice abstinence.

Measures taken to minimize these risks are detailed above in #8. Samples and clinical information will be stored and cared for with every precaution taken to ensure confidentiality of participant information. There will be no compensation except for a parking sticker and testing results will not be released to individual subjects. However if the patients require to be treated with Cimzia (anti-TNF $\alpha$ ), the medication will be provided to them free of charge up to 2 years. Subjects will not benefit directly, but receive medication.

## 12. Monitoring and Safety of Subjects

Possible adverse events that could be anticipated would be either complications arising from obtaining blood samples or breach of data security. While these events are unlikely, they would be immediately reported to the IRB. As above, all precautions will be taken to avoid adverse events, and any improvements in the sample collection and archival process that become available during the course of the study will be implemented (for example, new technology that allows the study of smaller amounts of blood sample, new widely available data security measures, etc.) Referring physicians will be charged with the continued monitoring of study participants as part of their routine care.

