#### 8. Special Precautions to be Taken by Researchers

The potential risks are limited to that associated with routine blood draw, and the collection and storage of personal health information.

A possible risk of the research is that your participation in the research or information about you and your health might become known to individuals outside the research.

[name] will obtain consent from patients with an informed consent document and authorization form. Copies of these forms will be added to each patient's permanent medical record. Drawn peripheral blood samples will be stored and a assigned a code, which will be identifiable only by the master list. The master list will be kept in a locked cabinet or a computer that would need a password to be accessed. Besides the PI and the key personnel, nobody will have access to the locked cabinet or the computer where the information is stored. The consent forms, authorization forms, and the coded index will be only available to the PI and key lab personnel involved in the project. The consent forms and authorization forms will be kept in a locked cabinet. The data will be kept on a secured server accessible only to the PI and key lab personnel involved in the project. The data recorded in the lab books and computer records will refer to the subject's code, not the name. Data shared with collaborators will be identified only by the code. The patients will never be identified in any publication.

When the results of the research are published or discussed in conferences, no information will be included that would reveal your identity.

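### Sections 8 and 12 recognise only blood-draw and data risks, Section 11 contradicts them, and no available text commits anyone to report a harm from study-supplied Cimzia

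*Combined protocol and SAP*

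**What the plan says.** Section 12 states which adverse events are expected: "Possible adverse events that could be anticipated would be either complications arising from obtaining blood samples or breach of data security". It calls them unlikely and adds that "they would be immediately reported to the IRB". It does not say who makes that report. This is the only mention of the IRB in the available text. On patient care, Section 12 says "Referring physicians will be charged with the continued monitoring of study participants as part of their routine care".

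Section 8 takes the same view of the risks: "The potential risks are limited to that associated with routine blood draw, and the collection and storage of personal health information". The rest of that section deals with consent, sample coding and confidentiality.

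Section 11 goes further. Of the side effects of Cimzia it says "these include serious infections, Invasive fungal infections, cases of lymphoma and other malignancies, Heart failure, Hepatitis B virus reactivation and Lupus-like syndromes", and it adds "Use of Cimzia may cause damage to the fetus". It then states: "Measures taken to minimize these risks are detailed above in #8". For patients who need Cimzia, "the medication will be provided to them free of charge up to 2 years".

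Other sections bear on the point:

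- Sections 2 and 9 plan Cimzia, provided to the study by UCB, for the 150 donors who do not respond to DMARDs. Section 2 describes the drug as FDA approved and standard of care, and schedules blood samples at onset, 3 months and 6 months.
- Section 4 excludes active infection and self-reported pregnancy.
- Section 5 makes abstinence obligatory on Cimzia; Section 11 only recommends it.
- Section 16 gives the patient's physician no further part in the research once routine care has provided the specimens.

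**The concern.** The sections that set the risk statement and the reporting rule read as if this were only a blood-sampling study. The section that lists the risks to subjects reads as if it were also a drug study, and the study does provide the drug. Taken literally, a bruise from venipuncture is reported to the IRB, while nobody is committed to report a serious infection, a malignancy or a pregnancy in a patient taking study-supplied Cimzia.

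What is at stake is oversight. The PI, whose study supplies the drug, and the IRB may not learn of such an event. An IRB that relies on Section 8 would also have a risk statement that the protocol itself contradicts.

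**Working it through.** **1. Donors exposed.** From Sections 2 and 9: 50 donors in remission on DMARDs + 150 donors on DMARDs plus Cimzia = 200, which matches the stated total. Share planned to receive study-supplied Cimzia: 150 / 200 = 75%.

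**2. The three risk statements side by side.**

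| Risk | Section 11 | Section 8 | Section 12 |
|---|---|---|---|
| Blood-draw complications | yes | yes | yes |
| Breach of data or confidentiality | yes | yes | yes |
| Serious infection, including invasive fungal | yes | no | no |
| Lymphoma and other malignancy | yes | no | no |
| Heart failure | yes | no | no |
| Hepatitis B reactivation | yes | no | no |
| Lupus-like syndrome | yes | no | no |
| Fetal damage | yes | no | no |

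Section 11 names 6 Cimzia harms, or 7 if invasive fungal infection is counted apart from serious infection. Section 12 covers 0 of them on either count. This shows which harms are left out; it says nothing about how often they would occur.

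**3. The pointer from Section 11 to Section 8.** Following it leads to consent forms, coded samples, a master list under lock or password, and restricted access. These are measures against a data breach. None is a measure against a drug harm.

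**4. Search for a reporter elsewhere.**

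- Sections 4 and 5 are rules for entry and conduct. They do not say who is told if an infection or a pregnancy occurs on drug.
- Section 12 assigns monitoring to referring physicians but gives them no duty to inform the PI or the IRB.
- Section 2 describes rheumatologists as collaborators, and Section 16 allows that some are key personnel. Neither gives them a reporting task.
- Section 13 gives subjects study telephone numbers, and Section 14 provides a clinical database. Either could carry news of an event, but neither obliges anyone to send it.

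Section 7, by its position, and the consent and authorization forms could not be checked.

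**5. Scale, for illustration only.** The documents give no event rates. Assume a risk p per patient of any one class of serious event. Expected events = 150p, and the chance of at least one = 1 − (1 − p)^150.

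| Assumed p | Expected events | Chance of at least one |
|---|---|---|
| 0.5% | 0.75 | 53% |
| 1% | 1.5 | 78% |
| 2% | 3.0 | 95% |
| 5% | 7.5 | over 99.9% |

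Across this assumed range it is more likely than not that a reporting rule would be needed at least once. The finding does not depend on this table.

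**The case against.** The strongest reply is that the plan separates care from research. Cimzia is approved and standard of care, Section 11 ties supply to patients who require it, and Section 16 says clinical care is the same whether or not a patient takes part. On that view the research is the blood draw and the data. Section 8 concerns precautions by researchers, and drug safety belongs to the referring physician. This is a coherent reading and it softens the point. It does not remove it: the study provides the drug, and Section 11 lists the drug's harms as risks to subjects and claims that Section 8 deals with them.

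A second reply is that a reporting clause may sit in Section 7 or in the consent forms. That could be so, and it limits how firmly the absence can be stated. It would not repair the conflict between Sections 8, 11 and 12, which is in visible text.

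A third is that the PI could hear of an event through the study telephone numbers, the clinical database, or a rheumatologist who is also key personnel. That stands as a possibility, but a possible route is not an assigned duty.

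**Conclusion.** The point holds as a cheap improvement. Sections 8 and 12 contradict Section 11, and Section 11's pointer leads to no drug-safety measure; confidence in this is high. No available text commits anyone to report a Cimzia event to the PI or the IRB; confidence in this is medium, for want of Section 7 and the consent forms. The gap applies to a planned 150 of 200 donors (75%). It touches patient safety oversight only, not the endpoint or the analysis.

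A reader might infer three stronger things that the documents do not support.

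- **That nobody watches these patients.** Section 12 gives continued monitoring to referring physicians, who can treat the patient and stop the drug.
- **That reporting Cimzia events is ruled out.** Section 12 is silent on other events; it does not forbid reporting them. Section 16 does not clearly end the physician's role before the month 6 sample.
- **That the gap opens after the month 6 sample, because supply can last up to 2 years.** The samples are not described as safety visits, the actual length of supply is not given, and the missing duty is the same before and after month 6.

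**What to change.** 1. In Section 12, add the Section 11 Cimzia harms and pregnancy as anticipated events. The treating rheumatologist reports them to the PI, and the PI to the IRB, for as long as study-supplied drug is being taken. If Section 7 already contains such a rule, a cross-reference and the added events are enough.
2. Ask about these events at the existing onset (baseline), 3 month and 6 month visits.
3. Correct the Section 8 sentence that confines the risks, and point Section 11 to the new measures. Settle whether abstinence is obligatory (Section 5) or recommended (Section 11).
4. Amend Section 16 so that the physician's reporting role is allowed.

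**Cost.** Wording in five sections (5, 8, 11, 12 and 16), plus matching consent text if the forms repeat the narrow risk statement. The checks number at most 150 × 3 = 450, all short and all at visits already planned. The downside is a small reporting burden on physicians and study staff.

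I would not require a check at every resupply. Dispensing is not described, so this would be new follow-up of unknown volume. Design, endpoint and analysis stay as they are.
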